6.13.8. Additional Safety Concerns

6.13.8.1. Columbia Suicide Severity Rating Scale

Suicidal ideation, suicidal behavior, and self-injurious behavior without suicidal intent occurring during treatment, based on the Columbia-Suicide Severity Rating Scale (C-SSRS), will be summarized by treatment. In particular, for each of the following events, the number and percent of patients with the event will be enumerated by treatment: completed suicide, nonfatal suicide attempt, interrupted attempt, aborted attempt, preparatory acts or behavior, active suicidal ideation with specific plan and intent, active suicidal ideation with some intent to act without specific plan, active suicidal ideation with any methods (no plan) without intent to act, nonspecific active suicidal thoughts, wish to be dead, and self-injurious behavior without suicidal intent. Although not suicide-related, the number and percent of patients with non-suicidal self-injurious behavior occurring during the treatment period will also be summarized by treatment.

In addition, the number and percent of patients who experienced at least one of various composite measures during treatment will be presented and compared. These include suicidal behavior (completed suicide, non-fatal suicidal attempts, interrupted attempts, aborted attempts, and preparatory acts or behavior), suicidal ideation [active suicidal ideation with specific plan and intent, active suicidal ideation with some intent to act without specific plan, active suicidal

ideation with any methods (no plan) without intent to act, non-specific active suicidal thoughts, and wish to be dead], and suicidal ideation or behavior.

The number and percent of patients who experienced at least one of various comparative measures during treatment will be presented and compared. These include treatment-emergent suicidal ideation compared to recent history, treatment-emergent serious suicidal ideation compared to recent history, emergence of serious suicidal ideation compared to recent history, improvement in suicidal ideation at endpoint compared to baseline, and emergence of suicidal behavior compared to all prior history.

Specifically, the following outcomes are C-SSRS categories and have binary responses (yes/no). The categories have been re-ordered from the actual scale to facilitate the definitions of the composite and comparative endpoints, and to enable clarity in the presentation of the results.

Category 1 – Wish to be Dead

Category 2 – Non-specific Active Suicidal Thoughts

Category 3 – Active Suicidal Ideation with Any Methods (Not Plan) without Intent to Act

Category 4 – Active Suicidal Ideation with Some Intent to Act, without Specific Plan

Category 5 – Active Suicidal Ideation with Specific Plan and Intent

Category 6 – Preparatory Acts or Behavior

Category 7 – Aborted Attempt

Category 8 – Interrupted Attempt

Category 9 – Actual Attempt (non-fatal)

Category 10 – Completed Suicide

Self-injurious behavior without suicidal intent is also a C-SSRS outcome (although not suicide-related) and has a binary response (yes/no).

Composite endpoints based on the above categories are defined below.

- Suicidal ideation: A "yes" answer at any time during treatment to any one of the five suicidal ideation questions (Categories 1-5) on the C-SSRS.
- Suicidal behavior: A "yes" answer at any time during treatment to any one of the five suicidal behavior questions (Categories 6-10) on the C-SSRS.
- Suicidal ideation or behavior: A "yes" answer at any time during treatment to any one of the ten suicidal ideation and behavior questions (Categories 1-10) on the C-SSRS.

The following outcome is a numerical score derived from the C-SSRS categories. The score is created at each assessment for each patient and is used for determining treatment emergence.

• Suicidal Ideation Score: The maximum suicidal ideation category (1-5 on the C-SSRS) present at the assessment. Assign a score of 0 if no ideation is present.

Comparative endpoints of interest are defined below. "Treatment emergence" is used for outcomes that include events that first emerge or worsen. "Emergence" is used for outcomes that include events that first emerge.

- Treatment-emergent suicidal ideation compared to recent history:
 An increase in the maximum suicidal ideation score during treatment (Visits Y1-Y2)
 from the maximum suicidal ideation category during the screening and lead-in periods
 (C-SSRS scales taken at Visits X1-X2). Recent history excludes "lifetime" scores from
 the Baseline C-SSRS scale or Baseline/Screening C-SSRS scale.
- Treatment-emergent serious suicidal ideation compared to recent history: An increase in the maximum suicidal ideation score to 4 or 5 on the C-SSRS during treatment (Visits Y1-Y2) from not having serious suicidal ideation (scores of 0-3) during the screening and lead-in periods (C-SSRS scales taken at Visits X1-X2). Recent history excludes "lifetime" scores from the Baseline C-SSRS scale or Baseline/Screening C-SSRS scale.
- Emergence of serious suicidal ideation compared to recent history:

 An increase in the maximum suicidal ideation score to 4 or 5 on the C-SSRS during treatment (Visits Y1-Y2) from no suicidal ideation (scores of 0) during the screening and lead-in periods (C-SSRS scales taken at Visits X1-X2). Recent history excludes "lifetime" scores from the Baseline C-SSRS scale or Baseline/Screening C-SSRS scale.
- Improvement in suicidal ideation at endpoint compared to baseline:
 A decrease in suicidal ideation score at endpoint (the last measurement during treatment;
 Visits Y1-Y2) from the baseline measurement (the measurement taken just prior to
 treatment; (Visit X2). This analysis should only be performed for a non-lifetime baseline
 measurement (i.e., having improvement from the worse event over a lifetime is not
 clinically meaningful). A specific point in time can be used instead of endpoint.
- Emergence of suicidal behavior compared to all prior history:

 The occurrence of suicidal behavior (Categories 6-10) during treatment (Visits Y1-Y2) from not having suicidal behavior (Categories 6-10) prior to treatment (Visits X1-X2). Prior to treatment includes "lifetime" and/or "screening" scores from the Baseline C-SSRS scale, Screening C-SSRS scale, or Baseline/Screening C-SSRS scale, and any "Since Last Visit" from the Since Last Visit C-SSRS scales taken prior to treatment.

Patients who discontinued from the study with no postbaseline C-SSRS value will be considered unevaluable for analyses of suicide-related events. Only evaluable patients will be considered in the analyses. Fisher's exact test will be used for treatment comparisons in the Placebo-Controlled period.

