#### 9.4.5. C-SSRS

Consistent with Food and Drug Administration (FDA) regulatory guidance (FDA 2012), any occurrence of suicide-related thoughts and behaviors will be assessed as indicated in the Schedule of Activities (Section 2). The Columbia Suicide Severity Rating Scale (C-SSRS) is a scale that captures the occurrence, severity, and frequency of suicide-related thoughts and behaviors during the corresponding assessment period. The scale includes suggested questions to elicit the type of information needed to determine if a suicide-related thought or behavior occurred.

The C-SSRS is available in an adult's and a children's version. There is no version of the C-SSRS designed for use in a cognitively impaired population such as patients with AD; therefore, the children's version will be used. Terms captured by the use of the C-SSRS children's version can be mapped to Columbia Classification Algorithm for Suicide Assessment (Posner et al. 2007), to facilitate future pooling of data.

The first time the scale is administered in this study (at Visit 2), the C-SSRS "Baseline/Screening" version will be used, and the findings will constitute the baseline assessment. The C-SSRS "Since Last Visit" version will be used for all subsequent assessments. The C-SSRS will be administered to the patient with the caregiver/study informant present, after the cognitive and functional assessments. Responses from both the caregiver/study informant and patient will be considered when administering the scale. If a suicide-related thought or behavior is identified at any time during the study, a thorough evaluation will be performed by a study physician, and appropriate medical care will be provided.

The Lilly Self-Harm Supplement should be completed every time the C-SSRS is administered. If, based on administration of the C-SSRS, it is determined that suicide-related behaviors have occurred, then the Lilly Self-Harm Follow-Up form will be used to collect additional information to allow for a more complete assessment of these behaviors.

Any clinically significant findings from the C-SSRS should be reported to the Sponsor or its designee as an AE via eCRF per Section 9.2.

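### SAP 6.13.8.1 gives no route for a suicide, or an attempt with no later C-SSRS, to enter the C-SSRS suicide-related counts

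*SAP*

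**What the plan says.** SAP 6.13.8.1 names one data source. Suicidal ideation, suicidal behavior and self-injury, "based on the Columbia-Suicide Severity Rating Scale (C-SSRS), will be summarized by treatment". The events listed for enumeration include "completed suicide, nonfatal suicide attempt, interrupted attempt, aborted attempt, preparatory acts or behavior". Completed suicide is Category 10 of the reordered scale. The suicidal-behavior composite is a 'yes' "answer at any time during treatment to any one of the five suicidal behavior questions (Categories 6-10) on the C-SSRS".

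The section then limits who is analysed: "Patients who discontinued from the study with no postbaseline C-SSRS value will be considered unevaluable for analyses of suicide-related events", and "Only evaluable patients will be considered in the analyses". Treatment groups are compared by Fisher's exact test in the Placebo-Controlled period.

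Protocol 9.4.5 describes how the data arise: "The C-SSRS will be administered to the patient with the caregiver/study informant present, after the cognitive and functional assessments". It also says that "The Lilly Self-Harm Supplement should be completed every time the C-SSRS is administered". The Self-Harm Follow-Up form is used when the C-SSRS shows that suicide-related behavior has occurred.

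In Protocol Tables 2.2 and 2.3 the C-SSRS is given at Visit 2 (baseline), at Visit 3 (Week 1), at each later visit that is not by telephone, at early discontinuation (ED), and at the follow-up 4 to 6 weeks after the last dose.

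**The concern.** A completed suicide cannot be reported by the patient at an interview. The plan nevertheless tabulates it as an answer on an interview-based scale and does not say how the answer is obtained after a death. The same difficulty arises for a patient who makes an attempt and does not return.

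In both cases the outcome itself causes the missing record, so the loss falls on the most severe cases. The completed-suicide row could show zero in every group when a suicide had occurred. The suicidal-behavior composite, the combined ideation-or-behavior composite and the measure of newly emerging suicidal behavior would omit the same patient. The C-SSRS table and the SAE table of one report could then disagree, with no rule for reconciling them.

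**Working it through.** The plan states no figure for suicide-related events, so there is none to reproduce. The check is to follow each kind of case through the rules and then to size the loss under stated assumptions.

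**1. What happens to each case**

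| Case | C-SSRS data available | Result under SAP 6.13.8.1 |
|---|---|---|
| Suicide before the first post-baseline C-SSRS (scheduled at Week 1) | Baseline only | Unevaluable: out of numerator and denominator |
| Suicide later, after 'no' answers | Earlier 'no' answers, no further interview | In the denominator as a non-event |
| Attempt survived; next, ED or follow-up C-SSRS attended | 'Since Last Visit' version covers the interval | Recorded, if that visit counts as during treatment |
| Attempt; both ED and follow-up C-SSRS missed | None after the event | Excluded or a non-event, as in the first two rows |

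The evaluability rule alone is narrow. It reaches only patients with no post-baseline C-SSRS at all, in practice those lost around or before Week 1 without an ED or follow-up assessment. The wider route is the definition of an event as a 'yes' on the scale, which applies at any time in the study.

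The third row carries a proviso. The comparative endpoints use unfilled placeholders for their visit windows (X1-X2 and Y1-Y2), and the section does not say whether ED and follow-up assessments are during treatment.

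**2. Whether another planned analysis rebuilds these counts**

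- SAP 6.13.2 and 6.13.3 tabulate deaths, SAEs and discontinuations due to AEs, with no C-SSRS condition. A suicide would appear there.
- Table AZET.SAP.2, the clusters of special interest, has no suicide or self-injury cluster. The comparison of suicidal behavior by treatment is therefore not reconstructed on the AE side.
- Protocol 9.4.5 sends clinically significant C-SSRS findings to the AE record. Nothing runs in the other direction.

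**3. Size**

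Inputs: 633 patients per group (SAP 5.2, planned). The suicide rate and the exposure are not in the documents. The assumptions are 10, 20 and 40 per 100,000 patient-years and 2,000 patient-years over all groups.

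Expected suicides = rate × patient-years:
- 10/100,000 × 2,000 = 0.2
- 20/100,000 × 2,000 = 0.4
- 40/100,000 × 2,000 = 0.8

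One event in a group of 633 is 1/633 = 0.16%; if it is missed, the row shows 0%. The documents give no rate for attempts followed by loss of contact.

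Two-sided Fisher's exact test, 633 per group, assumed counts, for illustration only:

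| Events (one group v the other) | p |
|---|---|
| 1 v 0 | 1.00 |
| 2 v 0 | 0.50 |
| 3 v 0 | 0.25 |
| 5 v 0 | 0.062 |
| 6 v 0 | 0.031 |

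Scoring one of six events as a non-event moves p from 0.031 to 0.062. With the one or two events that are plausible for completed suicide, the test says almost nothing either way. What is lost is the count.

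**The case against.** The strongest reply is that the trial has several ways to learn of these events.

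- **Survived attempts.** A patient who discontinues is due ED procedures and a follow-up 4 to 6 weeks after the last dose, both with a C-SSRS. Protocol 9.4.5 also takes the informant's responses into account. This stands: a reader might infer that attempts leading to withdrawal are generally lost, and the schedule does not support that. The loss requires both assessments to be missed.
- **Interval between interviews.** Because telephone visits carry no C-SSRS, interviews are up to 13 weeks apart (Weeks 26 to 39 and 52 to 65). A reader might take this as a period of undetected events. For survivors it is not one, because the 'Since Last Visit' version covers the whole interval and the telephone visits collect adverse events.
- **Other safety reporting.** A suicide is an SAE, as is an attempt that leads to hospitalization or is life-threatening, with 24-hour notification (Protocol 9.2.1). Vital status is sought for patients who cannot be contacted (Protocol 8.3). Deaths and SAEs are tabulated in the safety populations. This also stands: one cannot infer that a suicide would disappear from the trial's safety reporting.
- **Silence is not proof.** Completed suicide is a listed category, and sites may have instructions outside these documents for completing it after a death. That is possible, but the SAP should not depend on an unstated procedure when its own text names only the scale.
- **Early stopping.** SAP 6.1 says that no test will be interpreted as statistically significant. This removes any inferential consequence. It does not remove the need for correct safety counts, which remain an objective (SAP 4.5).

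What is left is a real but narrow gap: suicides, and attempts with no later C-SSRS, have no stated route into the C-SSRS rows.

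**Conclusion.** The point holds for the C-SSRS table and its composites only. Followed literally, SAP 6.13.8.1 excludes a suicide that occurs before the first post-baseline C-SSRS and scores a later one as a non-event. It treats an attempt the same way when the patient misses both the ED and the follow-up C-SSRS. This rests on the absence, in both documents, of any instruction to complete the C-SSRS after a death or to bring AE, SAE or death data into Categories 6 to 10.

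Few events are expected: 0.2 to 0.8 suicides under the assumed rates and exposure, plus an unknown number of attempts. The effect is on descriptive safety counts and not on a confirmatory test. It merits correction because the loss is caused by the outcome and the table claims to report that outcome.

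**What to change.** Revise SAP 6.13.8.1 as follows.

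1. Count a patient in Categories 6 to 10 and in the self-injury row if the event is on a post-baseline C-SSRS or is recorded as an AE, SAE or cause of death in the period.
2. Treat any such patient as evaluable whatever the C-SSRS status, and use the Safety – PC population as the denominator for these event rows. Keep the evaluability rule for the ideation measures only.
3. Define the period: fill in the visit-window placeholders and say whether ED and follow-up C-SSRS assessments count.
4. Reconcile the C-SSRS with AE, SAE and death data before database lock. The Self-Harm forms can help here, but they are completed with, or triggered by, the C-SSRS and so are not an independent source for a patient who had none.

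The cost is SAP wording, one merge and a reconciliation check. All the data are already collected, and no site procedure changes.

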6.13.8.2. Skin Examination

Skin color will be reported at baseline using Fitzpatrick Scale Rating. The frequencies of the Fitzpatrick Scale Rating (I, II, III, IV, V, and VI) will be displayed by treatment group.

Any hypopigmentation will be assessed by location, percentage of body surface area involvement, degree (partial/decreased pigmentation to complete depigmentation), and other findings in or around the hypopigmentation area (eg, redness or induration). A static physician's

global assessment (sPGA) will be used to determine the subject's overall hypopigmentation severity at a given timepoint using a visual analog scale (VAS) ranging from 0 to 100. In addition, subjects noted to have evidence of hypopigmentation will be asked to record how bothersome they find the hypopigmentation on a VAS ranging from 0 to 100. Additionally, the percentage of patients with emergence of greater than expected hair hypopigmentation will be summarized for patients 'no' at baseline if question is available on worksheet. Frequency tables and summary statistics for the continuous parameters will be presented by treatment group for the Safety-PC and Safety-DS populations.

In order to display any changes/deteriorations during treatment, the following will be reported: number of subjects for whom no hypopigmentation was observed at baseline, but for whom at least once after randomization hypopigmentation was observed during treatment (Placebo-Controlled or Delayed-Start); summary statistics for the difference of maximum value during treatment minus baseline value for percentage BSA of hypopigmentation,; shift table of baseline vs. maximum value during treatment for degree of overall lesion severity. Summary statistics for the change in overall severity (sPGA) and "how bothered is the patient" will be reported for patients with emergence of hypopigmentation, increased severity of hypopigmentation, or increased BSA during the study.

6.13.8.3. Eye Examination

Frequency tables will be produced for all time points for performance of eye examination, visual acuity examination, intraocular pressure examination, and slit lamp exam status and dilated fundus exam status (normal, abnormal – clinically not significant, and abnormal – clinically significant). Clinically significant abnormalities will be displayed together with the corresponding specifications of abnormalities in separate individual data listings including data from the Placebo-Controlled and Delayed-Start periods.

Summary statistics will be produced for the following continuous parameters: left eye total visual acuity score, right eye total visual acuity and both eyes score (scores expressed as logMAR calculated as the negative log (base 10) of the decimal scores) as well as left eye intraocular pressure and right eye intraocular pressure (both in mmHg). For visual acuity, "count fingers" will be given a decimal score of 0.01 and a logMAR of 2 (reference http://www.hicsoap.com/publications/ProperMethodforCalculating.pdf). "Light perception" and "no light perception" cannot be assigned decimal or LogMAR values and so are treated as missing in the mean change summary tables. Visual acuities of patients with these values at any time during the study will be provided in a separate listing.

In order to display any changes/deteriorations during treatment, the following will be reported: number of subjects with any abnormal finding (slit lamp examination or dilated fundus examination) documented during treatment that was not already present at baseline; summary statistics for the difference of maximum value during treatment minus baseline value for left eye total visual acuity score, right eye total visual acuity score, left eye intraocular pressure (mmHg), and right eye intraocular pressure (mmHg); and worst assessment of overall eye examination results during treatment with possible entries "unchanged", "new", "improved", and "worsened".

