### 9.4.9.1. Adverse Events of Special Interest

Adverse events of special interest will include:

- Adverse eye effects including retina (Section 9.4.7)
- Adverse skin effects including rash (Section 9.4.9.3) and hypopigmentation (Section 9.4.8)
- Peripheral nervous system, central nervous system and muscle effects
- Liver toxicity (Section 9.4.9 and Section 8.1.1)
- Cardiovascular (CV)-type events (including, but not limited to, orthostatic hypotension and QT prolongation) (Section 9.4.9.2)

The topics listed above, as well as new topics which may be subsequently determined by the Sponsor, will be subject to enhanced surveillance activities. Additionally, the topics above will be analyzed for presentation in the Clinical Study Report in accordance with the Statistical Analysis Plan (SAP).

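### The visual-acuity change tables omit eyes recorded as light perception or no light perception, and no eye output compares severe acuity loss by arm

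*SAP*

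**What the plan says.** SAP 6.13.8.3 (Eye Examination) summarises acuity for the left eye, the right eye and both eyes, with "scores expressed as logMAR calculated as the negative log (base 10) of the decimal scores", so a higher value is worse. Count fingers "will be given a decimal score of 0.01 and a logMAR of 2". Light perception (LP) and no light perception (NLP) "cannot be assigned decimal or LogMAR values and so are treated as missing in the mean change summary tables". The next sentence gives the alternative route: "Visual acuities of patients with these values at any time during the study will be provided in a separate listing".

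To display deterioration on treatment, the same section plans three outputs:

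- "summary statistics for the difference of maximum value during treatment minus baseline value for left eye total visual acuity score", with the same for the right eye and for intraocular pressure;
- "number of subjects with any abnormal finding (slit lamp examination or dilated fundus examination) documented during treatment that was not already present at baseline";
- "worst assessment of overall eye examination results during treatment with possible entries" of unchanged, new, improved and worsened.

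Protocol 9.4.9.1 lists "Adverse eye effects including retina" among the adverse events of special interest. Protocol 3.3 names retinal changes as a potential risk that is monitored by eye examinations.

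**The concern.** LP and NLP lie below count fingers. Under the rule, an eye that declines to count fingers enters the tables with a large worsening, while an eye that declines further contributes nothing at that visit. Whether a value is missing therefore depends on how bad it is. For any eye that reaches LP or NLP from a scored level, the omission can only make the arm look better.

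The maximum-minus-baseline summary is the natural place to see such a loss. The SAP does not say whether the missing-value rule applies there. Its reason for the rule, that these levels have no decimal or logMAR value, holds there too. Without a further rule, an eye that reached NLP would be represented by a milder earlier value, or by none.

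At stake is whether a reader of the tables could see an imbalance between arms in severe loss of vision, for a drug whose eye effects were singled out for enhanced surveillance.

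**Working it through.** **1. The plan's own figure.** logMAR = −log10(decimal score). For count fingers, −log10(0.01) = 2.0, as the SAP states. This is the worst level that receives a number.

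**2. One eye.** The documents give no baseline acuity and no score for LP or NLP. Assume a baseline of 0.1 and, for illustration, scores of 2.3 to 3.0.

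- Any LP or NLP eye has worsened by more than 2.0 − 0.1 = 1.9 logMAR.
- Take an eye at 0.1 at baseline, 0.3 at the first on-treatment examination and NLP at the second. If NLP is treated as missing, maximum minus baseline is 0.3 − 0.1 = +0.2. If NLP is scored, it is 2.3 − 0.1 = +2.2 up to 3.0 − 0.1 = +2.9.

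**3. When an eye has no change value at all.** In the Placebo-Controlled period, Protocol Table 2.2 schedules post-baseline eye examinations only at Week 52, Week 78 and early discontinuation. SAP 6.1.1 requires a post-baseline measurement before a change is counted. SAP 5.1 says that, after the futility stop, ongoing patients came to a visit run on the early discontinuation schedule. A patient stopped before Week 52 may therefore have a single scheduled post-baseline examination. If an eye is LP or NLP there, it has no acuity change.

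**4. Effect on an arm's mean.** Let k eyes (one per patient) be LP or NLP among n = 633, the planned number per group in SAP 5.2, and let the other eyes have a mean change of zero. Scoring the k eyes instead of omitting them raises the mean by k × (score − 0.1) / 633. The last column is Fisher's exact test, two-sided, for k of 633 against 0 of 633.

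| k | Score 2.3 | Score 3.0 | Fisher p |
|---|---|---|---|
| 1 | 2.2/633 = 0.0035 | 2.9/633 = 0.0046 | 1.00 |
| 3 | 6.6/633 = 0.0104 | 8.7/633 = 0.0137 | 0.25 |
| 5 | 11/633 = 0.0174 | 14.5/633 = 0.0229 | 0.062 |
| 10 | 22/633 = 0.0348 | 29/633 = 0.0458 | 0.002 |

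The shift is inversely proportional to n. If only half of the planned patients had a post-baseline eye examination, the largest entry would double to 2 × 0.0458 = 0.092.

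**5. Reading.** Even 10 such eyes barely move the mean, so the mean is a weak detector whether or not LP and NLP are scored. A count by arm is much more sensitive to the same 10 cases. The p-values only show this contrast; SAP 6.1 says that no test will be interpreted as statistically significant.

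**The case against.** A reader might infer that patients who go blind vanish from the plan's assessment of eye harm. The documents do not support that, for five reasons.

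- The rule is confined to the acuity mean change tables, and the value lost is one eye at one visit. The other eye and other visits remain.
- LP is not total blindness, and an eye already at LP or NLP at baseline would be left out too.
- The acuities of every patient with these values are listed.
- New slit lamp or fundus findings and the worst overall examination result do not depend on logMAR.
- Protocol 9.4.7 sends clinically significant eye findings with a diagnosis to be recorded as a pre-existing condition or adverse event. SAP 6.13.2 and 6.13.3 compare treatment-emergent and serious events, and the retinal disorders cluster, between arms by Fisher's exact test in the Placebo-Controlled period.

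It would also go too far to say that the SAP applies the missing-value rule to maximum minus baseline. It is silent on this. Finally, the plan is open about its reason, and any single number given to NLP would be arbitrary.

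All of this stands, and it keeps the point small. It does not close the gap. A listing is not a comparison by arm. Slit lamp and fundus results record structure, not vision. The overall examination category cannot separate a slight worsening from loss of useful vision, and the adverse event route depends on a diagnosis being made and reported. Protocol 10.3.4 foresees comparing proportions of treatment-emergent abnormalities for eye examinations, yet the SAP gives no such proportion for acuity. For skin, SAP 6.13.8.2 does plan a shift table of baseline against worst severity.

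**Conclusion.** The point holds in a limited form. The acuity mean change tables omit the two worst levels because they are the worst, so they lean toward less harm for eyes that decline to LP or NLP. How these levels enter maximum minus baseline is unspecified, and no planned output compares severe acuity loss by arm.

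The effect on the means is small: under about 0.05 logMAR for 10 eyes of 633. That figure rests on an assumed baseline of 0.1, assumed scores up to 3.0, no average change in the other eyes and the planned arm size. The documents give no event rate; few cases are presumed. The value of the change lies in making a by-arm count visible, since correcting the mean would achieve little. Priority is low.

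**What to change.** In SAP 6.13.8.3, before final unblinding:

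1. Add a by-arm table of the worst on-treatment acuity category per eye against baseline, for example a shift table. Make count fingers, LP and NLP the worst ordered categories, fix the bands for better acuity in advance, and show eyes already at LP or NLP at baseline separately.
2. State that an on-treatment LP or NLP counts as the worst value in the maximum-minus-baseline display. Since it has no number, show the eye in its own worst-category row and do not represent it by an earlier, milder value.
3. Footnote the mean change tables with the number of LP and NLP eyes omitted per arm.

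Keep the listing. No score needs to be invented for LP or NLP.

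The cost is one extra table, one sentence and one footnote, from data already collected. Cells may be sparse, so the table should be read descriptively, in line with SAP 6.1 and 6.13.
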